6.3 Further exploratory analyses

In addition to the main outcomes listed above, further exploratory analyses are planned as follows

• Difference in mean change in disease severity (SASSAD) at 4 weeks compared to

baseline. This outcome is included in order to capture speed of onset of benefit.

- Further within person analyses will be conducted comparing outcomes collected during the final 4-week period (12 to 16 weeks), with those collected during the initial 4 weeks of the study (0 to 4 weeks). Data collected for the active treatment group will provide an indication of the likely carry-over effect of this intervention, which will be useful in planning the design of future trials in this area. Data collected for the delayed treatment group will inform the analysis regarding speed of onset of improvement.
- Predictors of response model including baseline factors such as filaggrin status (see later section), baseline eczema severity, water hardness, swimming activity and time away from the home).

7. ELIGIBILITY CRITERIA

The intention is to keep entry criteria as broad as possible in order to improve the external validity of the trial and to boost recruitment.

7.1 Inclusion criteria

- Children aged 6 months to 16 years at baseline, with eczema as defined by the UK refinement of the Hanifin and Rajka diagnostic criteria ¹⁴.
- Eczema present at time of assessment (minimum SASSAD score of 10).
- Baseline water hardness of >200 mg/L of calcium carbonate.
- Home suitable for the installation of a water softening device (as assessed by water engineer)

Only one child will be enrolled per family. The choice as to which child becomes involved will be made by the parents and children involved, taking into account the inclusion criteria above.

7.2 Exclusion criteria

- Children who plan to be away from home for >21 days in total during the 16-week study period. This has been deemed necessary in order to ensure adequate exposure to the intervention. We will also aim to ensure children do not have a planned holiday in the 4 weeks prior to their 12 week assessment visit.
- Children who have taken systemic medication (e.g. Cyclosporin A, methotrexate) or UV light for their eczema within the last 3 months because of their long lasting effects.
- Children who have taken oral steroids within the last 4 weeks, or who, as a result of seeing a healthcare professional, have started a new treatment regimen for eczema within the last 4 weeks.
- Families who already have a water treatment device installed, including ion-exchange softeners, polyphosphate dosing units or physical conditioners.

8. SCREENING AND RECRUITMENT

8.1 Participants

Children aged 6 months to 16 years with atopic eczema will be enrolled into the study. A diagnosis of eczema will be standardised using the UK working party's diagnostic criteria for atopic eczema ¹⁴. It is anticipated that participants will be recruited at a rate of 4-5 per centre per month and that recruitment will take place over 18 to 20 months.

8.2 Setting

Recruitment will take place in eight secondary care referral centres in the UK serving a variety of ethnic and social groups and including both urban and peri-urban dwellings. All have predominantly hard water (although water in the Nottingham area is mixed). Inclusion criteria assume baseline water hardness of >200 mg/L for entry into the trial. The eight recruiting centres will be i) Queen's Medical Centre, Nottingham; ii) Barnet & Chase Farm Hospital, London; iii) Addenbrookes Hospital, Cambridge; iv) The David Hide Asthma and Allergy Research Centre, St Mary's Hospital, Isle of Wight Healthcare Trust, Isle of Wight, v) University Hospital of Leicester NHS Trust, vi) St Mary;s Hospital, Portsmouth, vii) United Lincolnshire Hospitals NHS Trust and (viii) The Royal London Hospital. All centres hold designated paediatric clinics in which children with eczema are commonly seen.

Participants will be informed of the trial in various ways. In order to "kick start" recruitment during the initial phase, patients who have been referred to the recruiting centres over the previous 12-18 months will be sent letters and information sheets about the trial. On-going recruitment will also take place through outpatient clinics, although children who have recently seen a dermatologist (and have started on a new treatment regimen), will not be able to enter the trial for at least 4 weeks. In addition, R&D approval will be sought from Primary Care Trusts local to the seven recruiting centres, and letters and information sheets sent to patients under the dermatological care of their GP. In addition, primary schools will be informed of the trial and efforts will be made to advertise the study through direct advertising in the local media, and on relevant websites. Recruitment in Nottingham will be limited to those areas with a hard water supply based on postcode areas.

8.3 Randomisation and blinding

Participants will be entered into a web-based randomisation programme by the Trial Manager, or Research Nurse. This will randomise them to one of the 2 treatment arms based on a computer generated code, using random permuted blocks of randomly varying size. This will be created by the Nottingham Clinical Trials Support Unit (CTSU) in accordance with their standard operating procedure, and held on a secure server. The randomisation will be stratified by age, disease severity (baseline SASSAD \leq 20, or SASSAD score \geq 20) and recruiting centre. Access to the sequence will be confined to the CTSU Data Manager. Allocation to treatment arms will be in the ratio 1:1 and the Trial Manager will access the treatment allocation for each participant by means of a remote,

internet-based randomisation system developed and maintained by the Nottingham CTSU. The allocation group will be indicated to the Trial Manager only after baseline data have been irrevocably entered into the randomisation programme. The sequence of treatment allocations will be concealed until interventions have all been assigned and recruitment and data collection are complete.

The research nurses will be blinded to treatment allocation throughout the study period and the trial statistician will analyse the results based on treatment code, using an analysis plan finalised prior to revealing the coded allocation sequence. Only after the analysis is complete will the actual treatment arms corresponding to treatment codes be revealed. The only study personnel in direct contact with study participants will be the research nurses and water engineers. The trial manager and study support staff at the co-ordinating centre in Nottingham will have telephone contact with parents of participants. Trial participants will continue to see healthcare professionals for their usual eczema care.

Since participants will not be blinded to the study intervention, an objective primary outcome has been chosen in order to minimise response bias, The primary outcome of disease severity, measured using the Six Area Six Signs Atopic Dermatitis scale (SASSAD) will be assessed by the research nurses who are blind to treatment allocation. This scale is based purely on physical examination of the skin and does not require input from the participants themselves. Other secondary objective outcomes include nocturnal movement (measured using accelerometers) and the use of topical therapy.

Participants will be discouraged from discussing which treatment they have received with the research nurse. In order to reduce the opportunity for 'un-blinding', telephone contacts will be conducted by the (un-blinded) trial manager whenever possible and participants will be reminded not to mention their treatment allocation to the research nurse prior to their assessment visits. The importance of maintaining 'blinding' will also be highlighted in the participant information sheets.

Integrity of information bias will be assessed using clinical photographs of a target lesion. These images will be taken at each assessment visit and graded remotely by 2 independent dermatologists. These dermatologists will not be aware of the study design, or of the assessment visit at which the image was taken. Should the two dermatologists score an image very differently, a 3rd dermatologist will be asked to adjudicate. This method of photo assessment worked well in the pilot study.

8.4 Screening

Screening for the trial will be a 3-stage process. Those who express a willingness to take part in the trial will be approached as follows (NOTE: the order of the contacts may vary depending on the recruitment route):

1. By telephone or postal questionnaire – participants will be sent a Participant Information Leaflet along with a screening checklist. This will be followed up by telephone to assess eligibility. Participants will give either written or verbal agreement at this time for the study's water engineer to visit their home.

- 2. Home visit by the engineer the home will be assessed for suitability of installation of a water softening device.
- 3. Appointment with the research nurse assessment of eligibility criteria and recruitment into the trial. This appointment will be carried out in outpatients or in the patient's home.

Consent will be taken by the research nurse prior to conducting the recruitment assessment. Five copies of the consent forms will be generated for: i) the participants; ii) the medical notes; iii) the child's GP; iv) the Trial Master File and v) the local Site File.

9. DATA COLLECTION

9.1 Data Collection Methods (summarised in Table 1)

9.1.1. Face-face interviews with the research nurse

These interviews will take place at baseline (recruitment visit), 4 weeks, 12 weeks and 16 weeks.

The visits will include the following:

- i. check of eligibility criteria (recruitment visit only)
- ii. baseline characteristics / demographics (recruitment visit only)
- iii. examining the child for disease severity (using the Six Area, Six Sign Atopic Dermatitis score)
- iv. eczema symptoms (POEM)
- v. interviewing the family for quality of life dermatitis family impact questionnaire and EQ-5D $\,$
- vi. willingness to pay for an ion-exchange water softener (recruitment and by letter sent at 10 -12 weeks)
- vii. digital image of nominated target lesion³
- viii.weighing medications.

9.1.2. Treatment diaries

Diaries will be used to capture:

- i. the number of days when active topical treatment (topical corticosteroids, tacrolimus or pimecolimus) is applied
- ii. whether or not treatment has needed to be "stepped up" if so, in what way and for how many days ("stepping up" treatment will be defined in advance by the parents in consultation with the research nurse)
- iii. daily global assessment of disease activity by child and parents
- iv. nights away from home

³ Target lesion nominated by research nurse in discussion with the child/parents.

- v. health service resource use
- vi. personal costs associated with the eczema
- vii. whether or not the accelerometers have been worn (weeks 1 and 12).

Items i) and ii) above will be used to calculate the number of totally controlled weeks (TCW) and well controlled weeks (WCW) during the study. Diaries will also be used to remind participants to check the salt levels in the machine and to return a sample of the water for testing in the laboratory every week.

9.2 Accelerometers

Night-time movement will be measured each night for a period of 1 week at the beginning of the study (week 1) and at the end of the 12-week study (week 12). Data will be stored on the ActiwatchTM units and downloaded onto a laptop computer at the subsequent assessment visits. Recordings will take place every night between the hours of 10pm and 6am, as used by other investigators⁶.

9.3 Telephone support

Participants will be contacted by the trial manager at 8 weeks in order to provide advice and support about the study.

9.4 End of Trial Follow-up Questionnaire

Parents of participants will be sent an end of trial follow-up questionnaire once all participants have completed the study. This will seek information about current eczema status, and whether or not they have a functioning water softener.

Table 1: Summary of schedule of assessment visits

| | BASELINE | Group A | "4 week" Appointment | "8 week" | "12 week" | Group A Un-installation | "16 week" |
|---|---|--|---|-------------------------------|--|---|---|
| | = Day ZERO | installation | rippointment | Reminder | Appointment | Group B Installation | Appointment |
| Water Engineer Home screening visit Home visit to assess suitability of residence for installation of softener Estimate salt requirements and assess availability of storage for salt supply Test water hardness | Research Nurse Recruitment Visit clinic appointment Baseline characteristics Eligibility criteria checked SASSAD POEM Utility measures (DFI and EQ-5D) Weigh medications UTP questionnaire Digital photo of index site Saliva sample Explanation and issue of Diary 1 Explanation of accelerometer (Actiwatch TM) Issue Water Softener Information sheet Randomisation | Water Engineer At 0–2 weeks ♦ Install unit (Group A) within 10 working days of DAY ZERO (date of recruitment visit) ♦ Advice given to reduce soap consumption etc. ♦ Issue water sampling containers + prepaid envelopes | Research Nurse Clinic appointment At 4–6 weeks ◇ SASSAD ◇ POEM ◇ Digital photo of index site ◇ Saliva sample (if not obtained at baseline) ◇ Collection of week 1 Actiwatch™ data ◇ Weigh medications ◇ Collection of Diary 1 and Issue of new Diary 2 | Trial Manager At 8 to 9 weeks | Research Nurse Clinic appointment At 12–14 weeks SASSAD POEM Utility measures Digital photo of index site Weigh medications Collection of Week 11-12 Actiwatch™ data and Actiwatch™ Collection of Diaries 2 Issue Diary 3 Explanation of cross-over phase | Water Engineer At 12–14 weeks ◇ Remove unit (Group A) within 10 working days of 12 week anniversary of installation ◇ Install unit (Group B) within 10 working days of 12 week appointment with RN; retest water hardness. ◇ Advice given to reduce soap consumption etc (Group B) ◇ Issue water sampling containers and pre-paid envelopes (Group B) | Research Nurse Water Engineer At 16 to 18 weeks Clinic appointment with Research Nurse to carry out: SASSAD POEM Utility measure Collection of Diary 3 Visit by Water Engineer to: Remove unit (Group B), if they do not wish to purchase unit, within 10 working days of 4 week anniversary of installation Reinstall unit (Group A) if they wish to purchase unit at first convenient time after 16 week appointment with RN. |

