13.2 Roles & responsibilities

The Chief Investigator will have overall responsibility for the design, maintenance and delivery of the trial, and will serve as the study guarantor to sponsors, funders and journals.

The Trial Manager will be responsible for all aspects of the day-to-day running of the trial

The research nurses will be responsible for identifying and recruiting suitable participants, for conducting skin assessments and liaising with the local engineers over visit dates and times (prior to randomisation). Since research nurses are responsible for conducting the blinded outcome assessments, contact after the initial recruitment interview will be kept to a minimum. Subsequent telephone follow-up will be conducted by the trial manager or study support staff at the co-ordinating centre in Nottingham.

The Clinical Trials Support Unit (University of Nottingham) will provide data management for the trial. This will include a web-based randomisation service (with telephone backup), database design, data entry and central data monitoring.

[name] at the MRC Clinical Trials Unit in London will prepare an analysis plan prior to analysis.

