3.2. Secondary Endpoints

- 1. The difference between baseline and week 12 of the proportion of time spent moving during the night. Movement will be captured for periods of one week at weeks 1 and 12, and will be measured using accelerometers (Actiwatch). These units are worn by the child in the same way as a wrist watch. Due to possible differences between the units every effort was made to ensure the children always used the same unit and where this was not the case this has been documented. A sensitivity analysis will be performed excluding those who did not use the same unit throughout the trial.
- 2. Difference in the proportion of children who report either a good or excellent improvement in eczema severity at 12 weeks (using a 5-point Likert scale). As these data were not collected¹, responders will be grouped into three groups; those who report a reasonable (≤20%), good (>20% and ≤50%) or excellent (>50%) improvement in SASSAD score at 12 weeks.
- 3. Amount of topical corticosteroid / calcineurin inhibitors used during the 12 week study period. This information is captured by weighing the medication at each visit and then summarised according to steroid strength to give the total amount used from baseline to week 12. Nurses will also be providing an indication of the level of accuracy of any estimates. A sensitivity analysis will be performed excluding those for whom the nurse is not confident about the amount of medication used.
- 4. Difference in Patient Oriented Eczema Measure (POEM). This scale is a well validated tool that has been developed to capture symptoms of importance to patients (rather than objective signs that are used in traditional severity scales, such as SASSAD).
- 5. Difference in the number of totally controlled weeks (TCW) and well-controlled weeks (WCW) based on the number of days with eczema symptoms and the number of days that topical treatment is applied up to primary endpoint at 12 weeks. This will be derived from the symptom diaries.
- 6. Difference in the mean change from baseline in the Dermatitis Family Impact (DFI) questionnaire at 12 weeks.

-

Omitted from CRFs to avoid unblinding of research nurses, and also on reflection this measure would be too open to bias in a single-blind study. Therefore improvement based on improvement in SASSAD score is preferable.

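### The blinded research nurse is assigned the cross-over explanation at the 12-week visit, which exposes the week-16 SASSAD and, because scoring order is not fixed, possibly the primary score

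*Combined protocol and SAP*

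**What the plan says.** **The blinding rule.** Families know their arm, so Protocol 8.3 relies on SASSAD scored by blinded nurses: "The research nurses will be blinded to treatment allocation throughout the study period".

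**The 12-week visit.** The research nurse's entry in Protocol Table 1 begins "Clinic appointment At 12–14 weeks SASSAD POEM Utility measures" and ends with "Explanation of cross-over phase".

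**What follows that visit.** Under Protocol 9.5, Group A parents are sent instructions for bypassing the unit and are asked to act on them as soon as they get home. The engineer then removes the unit. Group B has a unit installed.

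**How contact is otherwise handled.** Protocol 8.3 gives telephone contacts to the unblinded trial manager where possible, expressly to limit unblinding, and says that "participants will be reminded not to mention their treatment allocation to the research nurse prior to their assessment visits". Protocol 13.2 says of the nurses that "contact after the initial recruitment interview will be kept to a minimum".

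**Other nurse tasks.** Protocol 9.1.1 lists SASSAD, then POEM, then "interviewing the family for quality of life dermatitis family impact questionnaire and EQ-5D".

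**Further safeguards.**
- Suspected unblinding is logged (Protocol 13.6).
- Photographs of a target lesion are graded remotely by two independent dermatologists (Protocol 8.3).
- A sensitivity analysis leaves out children whose nurse became unblinded (SAP 8.4).
- Nurse unblinding before the primary measurement is a per-protocol violation (SAP 5).

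**The concern.** The blinded SASSAD is the trial's named protection against bias. The plan keeps nurses away from conversations about the softener, yet assigns them one whose subject is what happens to it next. Because that step is opposite in the two arms, an ordinary family question, such as when the unit will be taken out, gives the arm away.

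The score most clearly at stake is the week-16 SASSAD. If SASSAD is not scored first at week 12, the primary score is at stake as well.

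**Working it through.** This is mainly a question of who does what, and in which order. The arithmetic at the end only gives scale.

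**1. Does the explanation have to reveal the arm?** No. Both groups switch, so a neutral account is possible. However, no script or neutral wording is specified, and the family knows its own arm.

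**2. Week 12.** Table 1 lists SASSAD first and the explanation last, and Protocol 9.1.1 also puts SASSAD ahead of POEM and DFI. If this is the working order, the explanation cannot affect the primary score. No sentence makes it the working order.

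**3. Week 16.** The explanation is given at the week-12 visit, so every week-16 SASSAD comes after it. Re-ordering tasks within a visit does not change that.

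**4. Where the week-16 SASSAD is used.**
- Protocol 10.5: a paired t-test within each group compares the change from baseline to week 4 with the change from week 12 to week 16, for onset and carry-over.
- SAP 10.3, onset: a one-sample t-test for the delayed group over weeks 12 to 16. That sentence names no outcome; SASSAD is the likely one, since the preceding onset test uses it. SAP 3.3 makes this conditional on a benefit being found.
- SAP 10.3, carry-over: a plot of daily bother scores, which parents record. This does not depend on the nurse.

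**5. What the safeguards leave open.**
- Reminders not to disclose are weakened when the nurse opens the subject.
- Logging depends on the nurse noticing and reporting.
- Photographs cover one lesion, not six areas. Table 1 lists none at week 16, although Protocol 8.3 has them at each assessment visit.
- Both SAP analyses exclude children after randomisation. SAP 8.4 counts unblinding at any time in the trial, so it would also drop a child whose nurse learned the arm only after a properly blinded week-12 score. The SAP 5 criterion is limited to unblinding before the primary measurement.

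**6. Scale.** Inputs from Protocol 10.2: difference 20% × 20 = 4 points, SD 10, 5% significance (taken as two-sided), 90% power, 15% attrition.
- Plan's figure: n per arm = 2 × 10² × (1.960 + 1.282)² / 4² = 131.3, rounded up to 132. Total 264 / 0.85 = 310.6, or 311 (309.0 without rounding per arm). The stated 310 is reproduced.
- Evaluable children: 310 × 0.85 = 263.5. Standard error = 10 × √(2 / 131.75) = 1.23 points.
- Power of the SAP 8.4 sensitivity analysis if a share x is excluded, from Φ(4√(1 − x) / 1.23 − 1.96): 88.6% at x = 5%, 86.9% at 10%, 82.7% at 20% and 77.5% at 30%. The shares are assumed.
- Bias = share affected × mean shift in the arm contrast among those affected. With assumed shares of 20% and 40% and an assumed shift of 2 points: 0.2 × 2 = 0.4 and 0.4 × 2 = 0.8 points, or 10% and 20% of the 4-point target. On the week-12 contrast the two-sided 5% error rate, Φ(−1.96 + b/1.23) + Φ(−1.96 − b/1.23), would become about 6% and 10%. This applies only if the explanation comes before scoring.

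**The case against.** The strongest reply is that the explanation is listed after the primary score, can be given neutrally, and sits among several safeguards. Arm-specific bypass instructions are sent to parents and are not attributed to the nurse. The clear exposure is in analyses that are exploratory in the protocol and, in the SAP, tertiary and conditional on benefit. All of this stands, and it confines the point to a procedural weakness. It does not explain why a nurse who must stay blind holds this task when an unblinded trial manager is available.

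A reader might infer more in four places, and the documents do not support it:
- **That the primary result is compromised.** That requires the listed order to be broken, and nothing says it will be.
- **That the SAP itself treats these interviews as unblinding.** The footnote to SAP 3.2 says "Omitted from CRFs to avoid unblinding of research nurses", but it concerns one global-improvement item and adds a second reason, the item's openness to bias in a single-blind trial. The same SAP keeps POEM and DFI.
- **That nurses interview on family impact before the primary score, at week 4.** Table 1 lists POEM at week 4 but no DFI or EQ-5D.
- **That the SAP's carry-over analysis rests on nurse scores.** It uses parents' bother scores.

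**Conclusion.** The point holds as a conflict between a stated task and the plan's own blinding rules. The week-16 SASSAD is exposed in every case. The week-12 primary score is exposed only if SASSAD is not scored first, an order that the documents list but do not require.

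The size of any bias cannot be estimated: the documents give neither an unblinding rate nor a size of assessor bias, and the bias figures above rest on assumed values. The week-16 analyses are within-group, so a shift in the nurse's scoring would enter the estimated change directly, with no concurrent comparison in that analysis to offset it.

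The sample size is unaffected. The change is worth making because it is small and protects the trial's main defence against bias.

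**What to change.** 1. **Protocol Table 1.** Move "Explanation of cross-over phase" from the research nurse to the trial manager, by letter or telephone. Time it with the bypass information already sent to Group A parents, so that families have it by the time they return home from the 12-week visit. A message sent only after the visit would fit poorly with the Group A request in Protocol 9.5. The message should direct questions to the trial manager and repeat the request not to discuss allocation with the nurse.
2. **Protocol 9.1.1.** Require SASSAD and the photograph to be completed and closed before any interview or other conversation at each visit.

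Self-completion of POEM, DFI and EQ-5D is optional. It would cut nurse conversation further, perhaps at the price of some missing items.

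The cost is a minor amendment and one further letter or call per family, at most 310 in all, for a trial manager who already telephones families at week 8. No extra staff should be needed.

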9.5 Engineer's visits

Engineers will conduct a screening visit for potential trial participants in order to assess the suitability of their home for the installation of a water softener. A standard checklist will be prepared for this purpose. Any households which are not able to have a unit installed (for whatever reason) will not be enrolled into the study. The pre-recruitment visit will also assess the likely salt requirements of the family, and test water hardness.

If randomised to Arm A, an installation visit will take place as soon as possible following randomisation to treatment (ideally within 10 working days).

For the active treatment group parents will be sent information about how to bypass the unit and asked to do this immediately they return home after their child's 12-week assessment visit. Units will subsequently be removed by the water engineer as soon as possible (ideally within 5 working days) to ensure that the units cannot be turned on again during the final 4-week non-intervention period. If the family chooses to purchase a unit at a reduced price (£446.50) a unit will be reinstalled after they have completed the final 4-week non-intervention period of the study. Families in the active treatment group will send samples of water for hardness testing on a weekly basis throughout the 12 week period when the unit is installed. Those allocated to delayed treatment will receive an active unit at 12 weeks. This will then be removed after week 16 unless the family decides to purchase the unit. Families in the delayed treatment group will send samples of water for hardness testing on a weekly basis from weeks 13 to 16 inclusive.

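### Protocol Table 1 and Section 9.5 give different triggers and windows for removing the Group A softener, and Table 1 read literally allows removal up to about 14 days before the primary SASSAD

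*Combined protocol and SAP*

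**What the plan says.** The protocol describes the end of softening in Group A in two places.

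- **Table 1 (Section 9.4), un-installation column.** The column is headed "Water Engineer At 12–14 weeks", and the Group A unit is to be removed "within 10 working days of 12 week anniversary of installation". Bypass is not mentioned. The same cell ties installation in Group B to the nurse's 12-week appointment, so the two groups have different triggers.
- **Section 9.5 (Engineer's visits).** Parents receive bypass instructions and are "asked to do this immediately they return home after their child's 12-week assessment visit". Then: "Units will subsequently be removed by the water engineer as soon as possible (ideally within 5 working days"). The stated purpose of removal is that the unit cannot be switched back on during the last four weeks.

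The other timings come from Table 1. For installation: "Install unit (Group A) within 10 working days of DAY ZERO (date of recruitment visit"). For the visit that carries the primary outcome: "Clinic appointment At 12–14 weeks SASSAD POEM". For the last visit: "At 16 to 18 weeks Clinic appointment with Research Nurse".

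SAP Section 5 defines the per-protocol exclusions, and SAP Section 9.2 takes absence from home as the compliance measure. Neither refers to the date on which the unit was removed.

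**The concern.** One event has two clocks, installation date and assessment visit, and two windows, 10 and 5 working days. An engineer booking from the Table 1 entry alone could remove the unit before the child is scored.

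That would touch the primary contrast. Protocol Section 10.1 asks about 12 weeks of softened water against standard care, and the plan treats exposure just before the visit as important: Section 7.2 tries to keep planned holidays out of the preceding four weeks, and SAP Section 5 uses the same four weeks to define violators. How fast any benefit fades is one of the trial's own open questions (Section 10.1, item 5), so a gap before scoring cannot be assumed harmless.

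I found no step that links the removal booking to the assessment date. Section 13.1 has the water companies' co-ordinators arrange engineer visits, and Section 13.2 describes nurse liaison with engineers over dates only for the time before randomisation.

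If removal comes late instead, a clean off period in Group A rests on parents bypassing the unit and leaving it bypassed.

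**Working it through.** **The plan's own figure.** The difference is 0.20 × 20 = 4 SASSAD points, with SD 10, two-sided 5% (sidedness assumed for the main calculation) and 90% power. Per arm: 2 × (1.960 + 1.282)² × 10² / 4² = 131.4, so 132, or 264 in total. With 15% attrition: 264 / 0.85 = 310.6, so 311 against the stated 310. It reproduces. No removal date enters it, so this point leaves the sample size alone.

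**Inputs, in calendar days** (10 working days = 14 days, 5 working days = 7 days, public holidays ignored):

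- Installation I: day 0 to 14 (Table 1).
- Primary visit V: weeks 12 to 14, day 84 to 98 (Table 1). Counting from Day Zero is an assumption, because the table labels baseline as Day Zero but does not state the anchor for visits.
- Removal R under Table 1: from I + 84 to I + 84 + 14, so day 84 to 112 overall.
- Removal R under Section 9.5: from V to V + 7, if the ideal timing is met.

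**Removal minus visit (R − V):**

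| Reading | Earliest | Latest |
|---|---|---|
| Table 1, on or after the anniversary | 84 − 98 = −14 | 112 − 84 = +28 |
| The same, held to the column's weeks 12–14 | 84 − 98 = −14 | 98 − 84 = +14 |
| Table 1, visits counted from installation | 84 − 98 = −14 | 98 − 84 = +14 |
| Section 9.5 | 0 | +7 |

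If the window were read as either side of the anniversary with no other limit, the range would be −28 to +28. The column's own weeks bring that back to −14 to +14, so I use 14 days as the maximum gap before the visit.

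**Can both rules be met?** Not always, if visits run from Day Zero and removal follows the anniversary. A child with installation on day 14 and a visit on day 84 should ideally have the unit out by 84 + 7 = day 91 under Section 9.5, but the anniversary is 14 + 84 = day 98. Table 1 also conflicts with itself: installation on day 14 permits removal up to 14 + 84 + 14 = day 112, past the column's limit of day 98.

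**Would the SAP detect a 14-day gap?** Take installation on day 0, removal on day 84 and the visit on day 98.

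- The 75% criterion counts only the time during which the home has a unit. Fourteen days without one leave the denominator, so the child scores 84/84 = 100%. Even counted up to the visit, the figure is 84/98 = 86%.
- The other Group A criterion needs more than 2 affected days in every one of the four weeks before the assessment. A 14-day gap fills the last two weeks and leaves the first two untouched, so it cannot meet this criterion alone.

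**Off period.** Weeks 12 to 16 are 28 days. Within Table 1's own 12–14 week window the unit can stay in place for at most 14 of them. All 28 would need installation on day 14, a visit on day 84, removal on day 112 and that window ignored. For softening itself to continue, bypass must also be omitted or reversed. Section 9.5 schedules Group A water samples only for the 12 weeks with the unit installed, and the diary items in Section 9.1.2 include no bypass date.

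**The case against.** The best defence is that the texts can be read together. Table 1 is a summary, it places un-installation in the column after the 12-week appointment, and that appointment includes an explanation of the cross-over phase. Section 9.5 is the section on engineers' visits, gives the sequence, and uses the word subsequently for removal. On that reading the order is visit, bypass, removal, and the 14-day gap is a corner case that pairs the earliest installation and removal with the latest visit. This stands in part: early removal is possible, not expected. It does not dispose of the point, because the two columns carry the same 12–14 week window, the Table 1 entry makes no reference to the visit, and no precedence is stated.

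A reader might infer that softening in Group A runs on through the whole off period. The documents do not support that. Bypass under Section 9.5 ends softening on the visit day, and late physical removal alone does not restart it. Any overlap would reach only analyses that the protocol calls exploratory or tertiary (Sections 6.3 and 10.5) and that the SAP performs only if a benefit is found (Section 3.3).

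A reader might also blame this conflict for exposure at the primary visit ranging from 84 − 14 = 70 days to 98 − 0 = 98 days, that is 10 to 14 weeks. That range comes from the installation and visit windows and would remain after the removal rules were reconciled.

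**Conclusion.** The inconsistency is real and bears on the primary endpoint in one direction only. Read literally, Table 1 permits removal up to about 14 days before the primary SASSAD, whether visits are counted from Day Zero or from installation. Such a gap would not by itself trigger the SAP's exposure criteria, so it could affect both the ITT and the per-protocol comparison unless it were logged separately and judged a major deviation.

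In the other direction, removal can fall up to about 14 days after the visit within Table 1's own window. This matters only if bypass fails, and only for exploratory or tertiary analyses.

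It would go too far to say that the primary result will be diluted. The documents show neither how many children would have an early removal nor how quickly an effect would be lost. The day counts assume that 10 working days are 14 calendar days and that removal follows the anniversary within the column's 12–14 weeks. No view is taken on which of the two rules is right.

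**What to change.** Reconcile Table 1 and Section 9.5 so that one trigger and one window govern the end of softening in Group A, and so that both places state the same order for the week-12 assessment, bypass and removal. State the day from which visits are counted. The choice of rule is for the trial team.

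Record the dates of installation, bypass, removal and assessment for each Group A child, and have the SAP say how they enter the per-protocol review. Softened-water exposure at the primary assessment is then known, and a gap before it can be seen.

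The cost is an edit to two protocol passages, an instruction to the engineers, a sentence in the SAP and a few extra dates on the forms. The sample size does not change.
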